## 4. STUDY DESIGN

This study will be a phase 4 open-label trial in which 628 Philippine infants 9 months of age will be randomized 1:1 to one of two arms:

- Group 1: 314 children receiving one dose of CD-JEV vaccine and one dose of MMR vaccine concurrently at enrollment; Group 1 will also receive a second dose of MMR per the routine immunization schedule at D84 (12 months of age).
- Group 2: 314 children receiving one dose of MMR vaccine at enrollment and one dose of CD-JEV 56 days later. Group 2 will receive a second dose of MMR per the routine immunization schedule at D84 (12 months of age).

Following receipt of study vaccine, infants will be monitored for immediate reactions during the first 30 minutes, solicited injection site and systemic adverse reactions for 14 days, unsolicited adverse events for 28 days, and serious adverse events throughout the duration of the study. All safety events will be identified or observed by study staff and/or reported by a parent. Solicited adverse reactions will be recorded by the parent on diary cards or assessed during clinic visits. Study staff will make a follow-up call to the participant's parent/guardian 2 days post vaccination (+3 days) to check on the welfare of the participant and ensure the diary card is being completed. The parent will return for a clinic visit 14 days post vaccination (+3 days) for the study staff to review the diary card, conduct safety evaluations, and review any adverse events. Information regarding unsolicited AEs will be collected during any scheduled or unscheduled clinic visit. Events will be graded for severity and assessed for relatedness to vaccination by the study clinician.

The study will be open-label; no placebo control will be employed. Due to the unequal number of injections per visit in each study arm, safety assessments will be unblinded.

Blood samples for serologic testing will be collected on Day 0, Day 28(+7), and Day 56(+7) for Group 1; and Day 0, Day 56(+7), Day 84(+7) for Group 2.

Baseline serologies will test for antibodies to JE, measles, mumps, rubella, and dengue virus. Antibody responses to CD-JEV will be tested 28(+7) days after vaccination, while antibody responses to the first dose of MMR will be tested 56(+7) days after vaccination. All laboratory testing will be conducted in a blinded fashion.

## 4.1. Study Site

The study will be conducted at RITM, [name]. Established to spearhead the planning and implementing of research programs for infectious and/or tropical diseases, RITM's core research facilities are equipped with ample technical support for the conduct of valid and reliable scientific investigations. With a 35-bed research hospital consisting of an intensive care unit, wards, and isolation room, the hospital provides care of patients needing tertiary management of infectious and/or tropical diseases. The research hospital has a clinical and a blood-banking laboratory.

Recruitment of study participants will be conducted at the Putatan Health Center and Bayanan Health Center, two barangay health centers located near RITM. A barangay is the smallest local government unit in the Philippines and is very similar to a village or town. Each barangay health center is headed by a physician and is supported by health workers composed of nurses, midwives, and dentists. RITM will provide medical care in collaboration with the participating clinics or through its medical facility free of cost. All the participants will be encouraged to seek care at the local clinic or RITM for any medical problems, whether minor illness or urgent care. Both health clinics are within 5 kilometers of RITM, which is equipped to handle any care that may be needed in the case of an emergency.

## 5. STUDY ENROLLMENT AND WITHDRAWAL

### 5.1. Participant Inclusion Criteria

Each participant receiving study vaccines must satisfy all of the following inclusion criteria at study entry:

- Age 9 months to <10 months at the time of enrollment.
- Residence in the study area.
- At least one parent or guardian willing to provide written informed consent.
- Generally healthy and free of obvious health problems as established by medical history, physical examination, and clinical judgment of the investigator.
- A parent or guardian is willing to attend all planned study visits and allow home visits and phone contacts, as required by the protocol.

### 5.2. Participant Exclusion Criteria

No participant receiving study vaccines may have any of the following exclusion criteria at study entry:

- Previous receipt of any measles-mumps-rubella containing vaccine.
- Previous receipt of any Japanese encephalitis vaccine.
- History of measles, mumps, rubella, or Japanese encephalitis infection.
- Administration of any other vaccine within 28 days prior to administration of a study vaccine or planned vaccination of any vaccine other than catch-up doses of routine EPI vaccines or oral polio vaccine during the 28 days after study vaccination.
- History of allergic disease or known hypersensitivity to any component of the study vaccines and/or following administration of vaccines included in the local program of immunization.
- Use of any investigational or non-registered drug within 90 days prior to the administration of

study vaccines or planned administration during the study period.

- Administration of immunoglobulins and/or any blood products within 90 days prior to the administration of study vaccines or planned administration during the study period.
- Chronic administration (defined as >7 days) of immunosuppressing or other immune-modifying agents for 14 days before or after vaccination (including systemic corticosteroids equivalent to prednisone  $\geq 0.5$  mg/kg/day; topical and inhaled steroids are allowed).
- Primary or acquired immunodeficiency, including HIV infection, or a family history of congenital or hereditary immunodeficiency as reported by parent.
- Acute or chronic, clinically significant pulmonary, cardiovascular, hepatic, or renal functional abnormality, as determined by medical history or physical examination, which in the opinion of the study physician, might interfere with the study objectives.
- Severely malnourished infants as measured by the World Health Organization weight-for-height tables (Z-score < -3).
- Any condition or criterion that, in the opinion of the study physician, might compromise the well-being of the participant, compliance with study procedures, or interpretation of the outcomes of the study.
- Acute illness at the time of enrollment defined as the presence of a moderate or severe illness with fever (axillary temperature  $\geq 38.0^{\circ}\text{C}$ ) or without fever (severity determined at the discretion of the study physician).

Acute illness is a temporary exclusion. Vaccination should be postponed at least 7 days after recovery. A visit for reassessment may be scheduled 7 days or more after temporary exclusion illness is resolved. Eligibility for study participation must be reassessed again at the next visit

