### 7.3. Eligibility/Enrollment/Baseline

For participants in the two groups, the following activities will occur at the time of eligibility assessment (Eligibility Assessment/Enrollment/Allocation/Blood Sample/Vaccine Administration):

1. At the designated location for vaccination, the parent will be interviewed to collect baseline information including demographic (age and gender) and health (known medical conditions and allergies including medications taken) information in order to confirm eligibility.
2. Qualified study staff will perform a physical examination of the child. Results will be reviewed by study staff and with the participant's parents to confirm eligibility prior to conduct of further procedures.
3. Based on collected information, inclusion/exclusion criteria will be verified and eligibility confirmed.
4. If eligible, the participant will be allocated into Group 1 or 2 according to the allocation process and given a unique participant ID number.
5. Prior to administration of the vaccine, a specimen of 3-5 mL of blood will be collected for baseline testing.
6. Study vaccine will be allocated to the participant per the allocation sequence and the child will receive the assigned study vaccination into the anterolateral aspect of the upper thigh.
  - a. Group 1 will receive MMR vaccine subcutaneously into the anterolateral aspect of the left upper thigh and CD-JEV subcutaneously into the anterolateral aspect of the right upper thigh.
  - b. Group 2 will receive MMR vaccine subcutaneously into the anterolateral aspect of the left upper thigh.
7. The parents will be asked to wait with the child in the clinic for 30 minutes after the vaccination(s), so that the study staff can observe for immediate reactions. If the child experiences an adverse reaction or an SAE during this time period, he/she will be treated or referred as appropriate, and the event will be recorded.
8. The parents will be given a study identification card that indicates that the child has been enrolled in a research study. The card will contain the following information:
  - Name, address, and contact phone numbers of the investigator and local study staff.
  - Child's unique study participant number.
  - Indication that the child is in a vaccine trial and a request that medical personnel who provide care to the child report any suspected adverse events and any abnormal or unusual clinical findings to the investigator.

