### **7.7.2. Group 2 Visit to Collect Serum and Provide CD-JEV (D56+7)**

1. At the designated location for vaccinations/blood draws, the participant's identity will be confirmed.
2. Study staff will review interim medical histories and concomitant medications with the participant since the last visit to the study clinic.
3. Qualified study staff will perform a physical examination of the child. Results will be reviewed by study staff and with the participant's parents.
4. The parents will be asked if the child experienced any adverse reaction or SAE and/or sought medical care since the last visit.
7. Before administration of vaccine, a specimen of 3-5 mL of blood will be collected for anti-measles, anti-mumps, anti-rubella, anti-JE testing, and anti-dengue.
5. The child will receive CD-JEV into the anterolateral aspect of the right upper thigh.
6. The parents will be asked to wait with the child in the clinic for 30 minutes after the vaccination, so that the physician can observe for immediate reactions. If the child experiences an adverse reaction or an SAE immediately following the vaccination, he/she will be treated or referred as appropriate.
7. Parents will be informed that they will be contacted in 2 days (+3 days) in order to check on the welfare of the participant, answer any questions about the diary card, and assess the occurrence of any local or systemic reactions.
8. The parents will be given a diary card and trained on how to record solicited and unsolicited adverse events occurring within 14 days post vaccination.
9. An appointment will be made to visit the clinic 14 days after vaccination (+3 days) for a follow-up visit.

10. Parents will be reminded to seek medical care as appropriate and inform the study clinician as soon as possible in the event of an adverse reaction or SAE. If the child visits a health care provider, the parents should be sure to inform him/her of the child's participation in the study and present the provider with contact information for the investigator as indicated on the study identification card. Additionally, the parents will be reminded to inform the study clinician that the child has visited a health care provider

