### **9.2. Methods and Timing for Assessing, Recording, and Analyzing Safety Parameters**

#### **9.2.1. Adverse Events**

An adverse event is defined as any untoward medical occurrence in a patient or clinical investigation participant administered a pharmaceutical product, which does not necessarily have a causal relationship with this treatment. An AE can therefore be any unfavorable and unintended sign (including an abnormal laboratory finding), symptom, or disease temporally associated with the use of a medicinal product, whether or not considered related to the medicinal product. The occurrence of an AE may come to the attention of study personnel during study visits and interviews of a study participant presenting for medical care.

Information to be collected on adverse events includes event description, date of onset, clinician's assessment of severity, relationship to study product (assessed only by those with the training and authority to make a diagnosis), and date of resolution/stabilization of the event.

Any medical condition that was present at the time that the patient was enrolled should not be reported as an AE. However, if it deteriorates during the study safety recording periods, it should be recorded as an AE.

AEs should be graded for severity and relationship to vaccine.

**Severity of Event:** Any AE which is not a local and systemic sign or symptom occurring within 14 days of vaccination will be assessed to quantify intensity using the following guidelines:

Grade	Categorization	Definition
Grade 1	Mild	Symptoms causing no or minimal interference with usual social & functional activities with intervention not indicated
Grade 2	Moderate	Symptoms causing greater than minimal interference with usual social & functional activities with intervention indicated.
Grade 3	Severe	Symptoms causing inability to perform usual social & functional activities with intervention or hospitalization indicated.
Grade 4	Potentially life-threatening	Symptoms causing inability to perform basic self-care functions with intervention indicated to prevent permanent impairment, persistent disability, or death.

*\*Intervention defined as medical, surgical, or other procedures recommended or provided by a healthcare professional for the treatment of an adverse event.*

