### **9.2.3. Reactogenicity**

Reactogenicity post-vaccination will be assessed from 30 minutes through 14 days following vaccination. All solicited local and systemic signs recorded from 30 minutes through 14 days post vaccination will be considered “related” to study vaccination. The parent will use a structured reactogenicity diary card for recording solicited (pre-listed) and unsolicited reactogenicity. Any reactogenicity continuing beyond 14 days will be documented as an adverse event and followed until resolution.

Any reactogenicity will be managed in accordance with good medical practices by the clinical study site team who will assess and treat or refer the child for medical care as appropriate. If needed to monitor or treat reactogenicity, additional study visits may be conducted. If any acute treatment or medical care is required as a result of harm caused by the study vaccine or study procedure, this care will be provided by the site free of charge. All children reporting reactogenicity will be followed clinically until the condition resolves (returns to baseline) or stabilizes. Conditions likely to be related to the product, whether serious or not, which persist at the end of the trial will be followed up by the study clinician until resolution or stabilization.

The parents of infants enrolled in this study will be instructed to contact the study site staff to report any reactogenicity of concern that their child experiences. In the case of a life-threatening event, they will be instructed to seek immediate emergency care. Where feasible and medically appropriate, parents will be encouraged to seek medical care for the child at the RITM clinic, and to request that the study physician be contacted upon their arrival.

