#### Table 1. Outline of study visits and activities

#### STATISTICAL ANALYSIS PLAN

	On or b	Group 2										
	fore D0	D0	D2 (+3)	D14 (+3)	D28 (+7)	D56 (+7)	D58 (+3)	D70 (+3)	D84 (+7)	D86 (+3)	D98 (+3)	D112 (+7)
Obtain informed consent	x											
Collect baseline demographic information		х										
Collect/review medical history		х										
Perform physical examination		х		x	х	x		х	х		x	х
Check/confirm inclusion/exclusion criteria		х										
Collect serum for serology testing		х				х			х			
Administer dose of MMR		х							х			
Administer dose of CD-JEV						x						
Observe for immediate reactions for 30 minutes		х				х			х			
Provide diary card to parent/guardian		х				х			х			
Call participant to inquire about child's well-being			х				х			х		
Collect diary card and review reported adverse events				х				х			х	
Record reported adverse events		х			х	x			х			х
Record reported serious adverse events		х	x	x	х	x	x	х	х	х	x	x
Exit participant from study												х

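### Illness is screened at Day 0 only and solicited signs have no per-dose baseline, so signs that began before Group 2's Day 56 CD-JEV dose can be counted as reactions to it

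*Protocol*

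**What the plan says.** **Entry conditions.** Protocol 5.2 opens its list with "No participant receiving study vaccines may have any of the following exclusion criteria at study entry", so the whole list is tied to entry. Its last item is "Acute illness at the time of enrollment defined as the presence of a moderate or severe illness with fever", or without fever where the physician judges the severity sufficient. The note below the list adds "Vaccination should be postponed at least 7 days after recovery" and then calls for eligibility to be reassessed.

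**Where the check is made.** Protocol 7.3 has an explicit step before the Day 0 vaccination: "Based on collected information, inclusion/exclusion criteria will be verified and eligibility confirmed". In SAP Table 1 the row "Check/confirm inclusion/exclusion criteria" is marked once per group, at Day 0.

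**The Day 56 dose.** Protocol 7.7.2 lists interim history, medication review, physical examination, a question on adverse events and a blood sample. Then: "The child will receive CD-JEV into the anterolateral aspect of the right upper thigh". No eligibility or deferral step appears. The Day 84 MMR visits (7.10.1 and 7.10.2) are written the same way.

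**Counting rules.** Protocol 9.2.3 states: "All solicited local and systemic signs recorded from 30 minutes through 14 days post vaccination will be considered" related to vaccination. Protocol 9.2.1 states: "Any medical condition that was present at the time that the patient was enrolled should not be reported as an AE", unless it worsens. Protocol 8.1.3 has onset and resolution dates recorded for solicited signs. SAP 7.2 tabulates reactions *occurring* between 30 minutes and 14 days after each vaccination. It does not mention signs already present at the dose.

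**The concern.** Secondary objective 6 describes safety when the vaccines are given together and apart. For CD-JEV, the concurrent doses all follow a written check that removes moderate and severe acute illness, and the separate doses follow none. A child who started coughing on Day 54 and still coughs on Day 57 has a solicited sign recorded inside the 14-day window. Under 9.2.3 that cough is related to CD-JEV. The exemption in 9.2.1 does not help, because the cough was absent at enrollment.

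If this happens more often in Group 2, reaction rates after CD-JEV alone are raised by background illness, and co-administration looks relatively better tolerated than it is.

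The text also leaves open what the entry conditions mean for later doses. The 28-day prior-vaccine condition in 5.2 refers to any study vaccine, yet it sits under the study-entry heading. Section 5.3.4 allows withdrawal of a child who has ceased to be eligible. The postponement note is worded generally but follows an enrollment criterion. Staff facing an ill infant on Day 56 could read these passages in different ways.

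**Working it through.** **1. The plan's own figure.** The design figure is 314 per group (Protocol 11.4, SAP 2.3). Inputs: rubella seropositivity 90% in both groups, margin 10%, one-sided 2.5%, individual power 95%, 20% non-evaluable. The Farrington-Manning calculation gives 251 evaluable per group, and 251 / 0.80 = 313.75, rounded up to 314. The figure reproduces. It rests on MMR serology, which in Group 2 is sampled before CD-JEV is given, so this point does not change it.

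**2. Following one pre-dose sign through the rules.**

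| Rule | Effect on a sign that began before the Day 56 dose |
|---|---|
| Protocol 5.2, 7.3, SAP Table 1 | Not applied at Day 56 |
| Protocol 7.7.2 | Can be noticed; no stated consequence |
| Protocol 9.2.1 exemption | Does not apply: anchored to enrollment |
| Protocol 9.2.3 | Related, if recorded after 30 minutes |
| Protocol 8.1.3 | Onset date held, but no rule uses it |
| SAP 7.2 | Unclear whether *occurring* means new or present |

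No rule clearly takes the sign out of the count.

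**3. Possible size.** The documents give no frequency of illness at Day 56. Let r be the true systemic reaction rate, equal in both groups. Let q be the excess share of Group 2 infants, over Group 1, with a sign already present at the CD-JEV dose and carried past it. Assume q is 2% to 5%, which is 314 × 0.02 = 6.3 to 314 × 0.05 = 15.7 infants. Assume r is 10% to 50%, and that pre-dose signs are independent of true reactions.

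- Observed Group 2 rate: r + q(1 − r)
- Artefact, Group 1 minus Group 2: −q(1 − r)
- 95% half-width with o the observed Group 2 rate: 1.96 × √[r(1 − r)/314 + o(1 − o)/314]

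| r | q | Observed Group 2 | Artefact (points) | 95% half-width (points) |
|---|---|---|---|---|
| 10% | 2% | 11.8% | −1.8 | 4.9 |
| 10% | 5% | 14.5% | −4.5 | 5.1 |
| 30% | 2% | 31.4% | −1.4 | 7.2 |
| 30% | 5% | 33.5% | −3.5 | 7.3 |
| 50% | 2% | 51.0% | −1.0 | 7.8 |
| 50% | 5% | 52.5% | −2.5 | 7.8 |

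Adding q directly would overstate the effect, because some of these infants would have shown the sign anyway.

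**4. Visit window, conditional.** Suppose the postponement note did cover later doses. An infant ill on Day 56 and recovered on Day 57 could be vaccinated on Day 57 + 7 = Day 64 at the earliest. Protocol Table 4 allows 56 to 63 days. The two provisions collide only under that supposition.

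**The case against.** Much can be said for the plan. Group 2 is not vaccinated unseen. Protocol 7.7.2 requires history, medication review and examination, 8.1.2 includes body temperature, and 6.2 calls for standard immunization practice. The postponement note can be read as covering any dose. The SAP's *occurring* can be read as new onset, and onset dates are there to support that reading. The Day 0 exclusion removes only moderate or severe illness, so a mild cough or a temperature of 37.5 to 37.9 °C (already Grade 1 fever under 9.2.3.1, but below the 38.0 °C in 5.2) can be counted after Day 0 doses in both groups. The Day 84 gap is the same in both groups. Safety is descriptive, with no between-group test, and the assumed artefact is smaller than the sampling half-width in every row of the table.

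All of this limits the point. What survives is that 9.2.3 turns on when a sign is recorded, not when it began, and that no text says how the onset dates are to be used.

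A reader might go further and infer that the co-primary comparison is damaged, because a postponed Day 56 visit would put Group 2's measles and rubella samples out of window. The Protocol Summary, which requires vaccines within their time intervals for the per-protocol sets, adds to that impression; 11.2.3 asks only for vaccines as assigned. The documents do not establish the inference. It needs the postponement rule to apply at Day 56, which is the unsettled question. For lost samples it also needs the blood draw to move with the dose, and 7.7.2 lists these as separate steps. Illness could delay Group 1's Day 56 visit too.

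**Conclusion.** The point holds as a gap in the counting rule for solicited signs, and the gap is unequal between groups for CD-JEV. It may raise descriptive systemic reaction rates after separate CD-JEV relative to concurrent CD-JEV, by 1.0 to 4.5 points under the assumptions above (q 2% to 5%, r 10% to 50%). Those inputs are assumptions, so bias is possible rather than shown.

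Three stronger readings are not supported:

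- that Group 2 goes unassessed before CD-JEV: it is examined and questioned, and what is missing is a criterion and a stated consequence;
- that measles, rubella or mumps non-inferiority is compromised: no effect on these comparisons is shown;
- that the JE immunogenicity comparison is biased in a known direction: any effect of illness at the dose on the JE response is of unknown size and sign, and the groups already differ by design in age and prior MMR when CD-JEV is given.

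The change is still worth making because it costs little and replaces a rule that mixes old signs with new ones.

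**What to change.** **Counting rule.** In SAP 7.2, for every dose in both groups (Days 0, 56 and 84), add a count of solicited systemic signs that were absent at that visit's pre-dose history and examination, or that later reached a higher grade. Show it beside the current count of all signs. Align Protocol 9.2.1 and 9.2.3 with this per-dose baseline; changing 9.2.1 alone would not do, since it governs adverse-event reporting and not the solicited count. The inputs (onset dates, pre-dose temperature, history and examination) are already collected. The SAP should also say how a sign without a recorded pre-dose grade is classed.

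Cost: protocol and SAP wording and one extra column in the safety tables. It should be settled before the first final analysis, which reports all safety data (SAP 3.7).

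**Reconciliation.** Protocol 5.2, 5.3.4, 7.7.2, 7.10.1, 7.10.2 and Table 4 should agree on whether the illness condition, the prior-vaccine condition and the postponement note apply to the Day 56 and Day 84 doses, and how that fits the visit windows. The clinical rule is for the sponsor to decide. If any dose may move, the text should say what happens to the Day 56 sample. Separating sample from dose could mean an extra visit and a JE and dengue baseline no longer taken at the dosing visit.
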